3 OBJECTIVES AND ENDPOINTS

Objectives	Endpoint/variable:
Primary objective:	•
To assess the effects of treatment with verinurad and allopurinol, allopurinol alone, and placebo on UACR at 6 months	Change from baseline in UACR at 6 months
Secondary objectives:	
To assess the effects of treatment with verinurad and allopurinol, allopurinol alone, and placebo on UACR at 12 months	Change from baseline in UACR at 12 months
To assess the effects of verinurad and allopurinol, allopurinol alone, and placebo on sUA	Change from baseline in sUA at 6 and 12 months
To estimate the dose-response relationship among 3 doses of verinurad and allopurinol and placebo on UACR and sUA	Change from baseline in UACR and sUA at 6 months
To assess the effects of verinurad and allopurinol versus placebo on kidney function	Change from baseline in estimated glomerular filtration rate at 6 and 12 months Change from baseline in creatinine at 6 and 12 months Change from baseline in cystatin-C at 6 and 12 months
CCI	

Table 4Objectives and endpoints

Objectives	Endpoint/variable:
CCI	
CCI	

Table 4Objectives and endpoints

AE Adverse event; ALT alanine transaminase; AST aspartate transaminase; CV cardiovascular; eGFR estimated glomerular filtration rate; NT-proBNP N-terminal pro-brain natriuretic peptide; PD pharmacodynamic; SAE serious adverse event; sUA serum uric acid; UA uric acid UACR urinary albumin to creatinine ratio Months 6 and 12 are specified as elapsed time after the 8-week titration period. Thus, Month 6 is at 34 weeks of treatment and Month 12 is at 60 weeks of treatment.

4 STUDY DESIGN

4.1 Overall design

4.1.1 Overview

This is a randomised, double-blind, placebo-controlled, parallel, global, dose-finding, Phase 2b study to assess the efficacy and safety of verinurad and allopurinol in patients with chronic kidney disease and hyperuricaemia. Patients who meet the eligibility criteria will be randomised in a 1:1:1:1:1 ratio to high, intermediate or low dose of verinurad plus allopurinol, allopurinol or placebo.

As of Protocol Version 5.0 and following a blinded interim analysis in September 2020, the study design was modified to include a new dosing regimen. All patients with Visit 9 (47 weeks) occurring after implementation of the amendment and IP is available (approximately 01 May 2021, ie, approximately half of planned patients randomized) will be treated with the new dosing regimen. Under the new dosing regimen all patients will continue with the same dose of verinurad and allopurinol as previously, except patients randomized to the low dose of verinurad (3 mg), which will be switched to treatment with 24 mg verinurad.

Also, following implementation of the amendment, all subjects will discontinue therapy after 60 weeks (Visit 10). Patients that have conducted Visit 10 before the implementation of the amendment will discontinue therapy at their next scheduled visit.

The new treatment regimen will be dispensed to patients for which Visit 9 falls on or after the last of the following dates:

- the date of availability at site of IP suitable for the new treatment regimen,
- the date of the Regulatory Authority approval of Protocol Version 5.0 in the respective country, and
- the date of the Ethics Committee/Independent Review Board approval of Protocol Version 5.0 in the respective country/site.

A patient in the new dosing regimen who is still on treatment, who has not been down-titrated and has signed Informed Consent Form (ICF) for the new dosing regimen, will receive the new treatment at Visit 9. Patients who do not consent should be discontinued from the study at a subsequent visit. If the patient has passed Visit 9 before the dates listed above, they will remain on the initial dosing regimen.

A total of 725 patients (145 per initial dosing regimen arm) at around 200 sites in around 15 countries will be randomised with equal probability to 1 of the initial dosing regimens 5 treatment arms.

For an overview of the study design see Figure 1, Section 1.3. For details on treatments given during the study, see Section 6.1 Treatments Administered.

For details on what is included in the efficacy and safety endpoints, see Section 8, Study Assessments and Procedures.

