A patient in the new dosing regimen who is still on treatment, who has not been down-titrated and has signed Informed Consent Form for the new dosing regimen, will receive the new treatment at Visit 9. Patients who do not consent should be discontinued from the study at a subsequent visit. If the patient has passed Visit 9 before the dates listed above, they will remain on the initial dosing regimen.

Additional details on treatment administration are included in Section 6.1.

Target patient population

The study will be conducted in male and female adults (\geq 18 years of age) with documented CKD who provide informed consent to participate in the study and are not pregnant. Eligible patients will have sUA concentrations \geq 6.0 mg/dL, eGFR \geq 25 mL/min/1.73 m² and a UACR between 30 mg/g and 5000 mg/g (inclusive). Patients should be receiving stable treatment of angiotensin converting enzyme inhibitor (ACEi) or angiotensin receptor blocker (ARB) for at least 1 month prior to entry into the study.

Patients with a prior history of gout will receive gout prophylaxis treatment with colchicine up to 0.6 mg once daily, as outlined in gout guidelines. If intolerance or other sound medical rationale exists for not using colchicine, the investigator may instead prescribe gout flare prophylaxis with steroids or non-steroidal anti-inflammatory drugs (NSAIDs), or avoid administering prophylaxis altogether. Prophylaxis against flares will be fully explained and discussed with the patient.

Study period

Estimated date of first patient enrolled: Q3 2019

Estimated date of last patient completed: Q4 2021

Number of patients

Total of 725 patients (145 per arm [initial dosing regimen]) at around 200 sites in approximately 15 countries will be randomised with equal probability to 1 of 5 treatment arms.

Treatments and treatment duration

Each patient will be treated as randomised with placebo, allopurinol, and/or verinurad plus allopurinol (3 doses) for 26 weeks at target dose after 8 weeks of titration to allow for assessment of the primary endpoint, UACR at 6 months. After Protocol Version 5.0 is implemented, patients will continue treatment at target dose for approximately 12 weeks after Visit 9, and will discontinue therapy at Visit 10. Patients who have already had IP administered at Visit 9 or a subsequent visit before Protocol Version 5.0 is implemented will discontinue IP at the next subsequent visit.

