Packaging and labelling	Verinurad capsules will be packaged in bottles. Each bottle will be labelled in accordance with Good Manufacturing Practice (GMP) Annex 13 and per country regulatory requirement	Allopurinol tablets will be packaged in bottles. Each bottle will be labelled in accordance with Good Manufacturing Practice (GMP) Annex 13 and per country regulatory requirement
Provider	AstraZeneca	AstraZeneca

Table 7Study treatments (after implementation of Protocol Version 5.0)

IP Investigational product

*3 mg verinurad capsules will only be used for down-titration for patients on the new dosing regimen as of Protocol Version 5.0.

**Patients on 24 mg verinurad need to take two 12-mg verinurad capsules. To match, patients in the other treatment arms must take 2 capsules to maintain the blind. Patients will be given two different bottles with differently coloured labels. Patients will be instructed to take one capsule from each of two different bottles every day. Patients who do not tolerate the new dosing regimen will be down-titrated to the initial dosing regimen (ie, patients on 24 mg will be down-titrated to 3 mg, and patients in other cohorts will not be dispensed the matching placebo capsule).

The verinural capsules release verinural over 8 h, hence the formulation is referred to as ER8 (Extended Release over 8 h).

Study treatments will be titrated in discrete steps as shown in Table 8. Titration steps will be spaced at 4-week (± 1 week) intervals to minimise the risk of skin reactions to allopurinol. Patients unable to tolerate the stepped dosage may be down-titrated only by reversing the assigned steps within treatment group, and verinurad and allopurinol dosages cannot be unpaired from the titration schedule. Patients who cannot tolerate the step-1 dose will be discontinued from IP and be followed for the remainder of the study.

At Visit 5 (approximately 8 weeks after randomisation) through Visit 9, titration to step-3 target dose will only be allowed if the patient's eGFR was \geq 30 mL/min/1.73m² at Visits 3 and 4.

When the new dosing regimen is introduced under Protocol Version 5.0, patients who were down-titrated due to intolerance in the initial dosing regimen will not switch treatment to the new dosing regimen. These patients will instead remain on the same treatment after Visit 9.

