Patients who do not tolerate the new dosing regimen will be down-titrated to the initial dosing regimen (ie, patients on 24 mg will be down-titrated to 3 mg, and patients in other cohorts will not be dispensed the matching placebo capsule).

Patients will only be allowed to switch to the new dosing regimen introduced under Protocol Version 5.0 if the patient's eGFR was \geq 30 mL/min/1.73m² at Visit 8. Management of patients with eGFR <30 mL/min/1.73m² at Visit 9 should be discussed with the medical monitor.

In case patient down-titration was done in error, the patient can be up-titrated only after consultation with the medical monitor.

	Step 1 - titration	Step 2 - titration	Step 3 - target dose
	(verinurad/allopurinol)	(verinurad/allopurinol)	(verinurad/allopurinol)
High Dose (mg)	3/100	7.5/200	12/300
Intermediate Dose (mg)	3/100	7.5/200	7.5/300
Low Dose (mg)	3/100	3/200	3/300
Allopurinol alone (mg)	0/100	0/200	0/300
Placebo (mg)	0/0	0/0	0/0

Table 8Titration schedule

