7.1.2 Study termination

The sponsor designee reserves the right to close the study site or terminate the study at any time for any reason at the sole discretion of the sponsor.

The study may be stopped if, in the judgment of AstraZeneca, trial patients are placed at undue risk because of clinically significant findings that:

- Meet individual stopping criteria or are otherwise considered significant
- Are assessed as causally related to study drug
- Are not considered to be consistent with continuation of the study

Regardless of the reason for termination, all data available for the patient at the time of discontinuation of follow-up must be recorded in the CRF.

In terminating the study, the Sponsor will ensure that adequate consideration is given to the protection of the patients' interest.

7.1.3 **Procedures for early discontinuation of study treatment**

The investigator should instruct the patient to contact the site before or at the time if study treatment is stopped. A patient who decides to discontinue study treatment will always be asked about the reason(s) and the presence of any AEs. The date of last intake of study treatment should be documented in the CRF (electronic or paper). All study treatment should be returned by the patient at their next on-site study visit or unscheduled visit. Patients permanently discontinuing study treatment should be given locally available standard of care therapy, at the discretion of the investigator.

Patients who discontinue study treatment will attend the end of treatment visit as soon as possible after treatment discontinuation. Discontinuation of study treatment, for any reason, does not impact on the patient's participation in the study. The patient should continue attending subsequent study visits and data collection should continue according to the study protocol (including a follow-up visit, but no need to do another end of treatment visit). If the

patient does not agree to continue in-person study visits, a modified follow-up must be arranged to ensure the collection of endpoints and safety information. This could be a telephone contact with the patient, a contact with a relative or treating physician, or information from medical records. The approach taken should be recorded in the medical records. A patient who agrees to modified follow-up is not considered to have withdrawn consent or to have withdrawn from the study.

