9.4.2.1 Primary efficacy analysis

The primary efficacy variable is the change from baseline in UACR at 6 months (Week 34, ie, 26 weeks of treatment following an 8-week titration phase). Primary analyses will be performed on the FAS population, which consists of all randomised patients regardless of

treatment discontinuation. In other words, post-discontinuation data will be collected and included in the primary analysis. Details on how to handle missing data will be provided in the SAP.

In addition to analysis of the hypotheses in Section 9.1, the primary efficacy variable will be analysed comparing (initial dosing regimen):

- Intermediate dose verinurad plus allopurinol with placebo
- Low dose verinurad plus allopurinol with placebo
- High dose verinurad plus allopurinol with allopurinol alone
- Intermediate dose verinurad plus allopurinol with allopurinol alone
- Low dose verinurad plus allopurinol with allopurinol alone

The analysis of change in UACR from baseline to Week 34 will be conducted on the natural log-transformed UACR values using a repeated measures mixed model.

The analysis model will include the fixed categorical effects of treatment, week, DM status yes or no, microalbuminuria or macroalbuminuria, NT-proBNP < or \geq 360 pg/mL, use of SGLT2 yes or no, and treatment-by-week interaction as well as the continuous fixed covariates of baseline log(UACR) and baseline log(UACR) by-week interaction. An unstructured matrix for the within patient error variance-covariance will be used. The denominator degrees of freedom will be calculated according to the Kenward-Roger method. A number of back-up models will be defined in the SAP in case of non-convergence of the preferred model or other issues.

The least squared mean change from baseline to 6 months in the log-transformed UACR will be calculated by treatment with its 95% confidence intervals. The least squared mean difference between the treatments will be calculated with its 95% confidence interval. P-values of the treatment differences between active treatment group and placebo/comparator will also be calculated.

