9.4.2.2 Secondary efficacy analyses

For the secondary variables at 6 months, the following comparisons will be made (initial dosing regimen):

- High dose verinurad plus allopurinol with placebo
- Intermediate dose verinurad plus allopurinol with placebo
- Low dose verinurad plus allopurinol with placebo
- High dose verinurad plus allopurinol with allopurinol alone
- Intermediate dose verinurad plus allopurinol with allopurinol alone
- Low dose verinurad plus allopurinol with allopurinol alone
- Allopurinol with placebo

For the secondary variables at 12 months, the comparison "24 mg (double dose)" versus "Placebo (double dose)" will be made. If the model will not provide reliable results (eg, due to no convergence), descriptive statistics only will be considered sufficient.

All secondary variables will be log-transformed before analysis.

Analysis of secondary variables at 6 and 12 months will be performed using a model similar to that used for the primary efficacy variable. Change from baseline and treatment comparisons will also be estimated similarly.

The dose response of verinural plus allopurinol on UACR and sUA will be evaluated using modelling, and the details will be provided in the SAP.

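### Declining the new dosing regimen is written as leaving the study, against the follow-up rule in Section 7.1.3, and the only named 12-month comparison appears to be selected after randomisation

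*Supplement*

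**What the plan says.** **Decliners.** Section 4.1.1 of the protocol (Version 5.0) gives the rule for patients who do not sign the new consent form: "Patients who do not consent should be discontinued from the study at a subsequent visit". The same rule stands in Sections 1.2 (twice), 4.1.2.9 and 6.1.1. No section says which subsequent visit is meant.

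**Patients who stop treatment.** Section 7.1 separates stopping treatment from withdrawing from the study. Section 7.1.3 applies to stopping for any reason: "The patient should continue attending subsequent study visits and data collection should continue according to the study protocol". It requires modified follow-up for patients who will not attend in person. Section 7.3 describes study withdrawal as the patient's own request.

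**Who receives the new regimen.** Visit 9 must fall on or after the local activation dates. Within that group, Section 1.2 limits the new treatment to a patient "who is still on treatment, who has not been down-titrated and has signed Informed Consent Form for the new dosing regimen". Section 6.1.1 adds a renal condition, which begins "Patients will only be allowed to switch to the new dosing regimen introduced under Protocol Version 5.0 if the patient's eGFR was" and sets the limit at 30 mL/min/1.73 m² at Visit 8. It also says that patients "down-titrated due to intolerance in the initial dosing regimen will not switch treatment to the new dosing regimen".

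**The 12-month analysis.** Section 9.4.2.2 states: "For the secondary variables at 12 months, the comparison '24 mg (double dose)' versus 'Placebo (double dose)' will be made". No other 12-month comparison is named. Under Section 6.1.1 two capsules are taken only in the new regimen. Section 9.4.2 makes the Full Analysis Set (all randomised patients) the default, and Section 9.4 leaves populations and missing data to the SAP, which is not among the documents.

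**The concern.** Declining a new dose is not the same as declining to be measured. The protocol keeps a patient who stops treatment because of an adverse event under observation, yet it removes one who merely declines the amended regimen. For the primary analysis Section 9.4.2.1 says that "post-discontinuation data will be collected and included in the primary analysis". No such assurance is given for Week 60, and data that were never collected cannot be recovered by any later analysis plan.

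The second worry is who remains in the double-dose groups. The calendar cut-off does not depend on arm. Being on treatment, not being down-titrated, having adequate Visit 8 eGFR and consenting all arise after 34 to 47 weeks of randomised treatment. The protocol gives reasons why they could differ by arm. Section 2.3 names creatinine elevation as the main toxicity of verinurad given alone and skin reaction as the main risk of allopurinol, and Section 7.1 stops treatment for the latter. If they do differ, the two groups may differ in prognosis before any 24 mg capsule is taken. At stake is the only efficacy comparison of 24 mg that the protocol names, at a time point that Section 4.2 calls a key secondary objective.

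**Working it through.** **1. The two rules side by side.**

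| Event | Consequence | Week 60 data |
|---|---|---|
| Stops treatment for any reason (7.1, 7.1.3) | Stays in the study, visits or modified follow-up | To be collected |
| Down-titrated, not switched (6.1.1, 4.1.2.10) | Stays on same treatment | To be collected |
| Visit 8 eGFR below 30 (6.1.1) | Not switched; medical monitor consulted if eGFR is below 30 at Visit 9 | Not excluded by any rule |
| Declines new consent (1.2, 4.1.1, 4.1.2.9, 6.1.1) | Discontinued from the study | Uncertain; depends on which visit |

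Only the last row can end data collection. Patients in the other rows should have Week 60 data but appear to fall outside the double-dose groups.

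**2. The plan's own figure (Section 9.2).** Inputs: 145 per arm, difference 0.29 on the ln scale, SD 1.0, two-sided alpha 0.1.

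Power = Φ(0.29 / √(2/145) − 1.645) = Φ(2.469 − 1.645) = Φ(0.824) = 79.5%, against the stated 80%. It reproduces. No figure is given for Week 60.

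**3. Precision at Week 60.** Assumption: half of each arm has Visit 9 after activation, from the loosely worded half in Section 4.1.1. That is 725/2 ≈ 362 patients, or 145/2 = 72.5 per arm. Difference, SD and alpha as above; half-width = 1.645 × √(2/n).

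| Further share excluded (assumed) | n per arm | Power for 0.29 | 90% CI half-width (ln) |
|---|---|---|---|
| 0% | 72.5 | 54.0% | 0.273 |
| 10% | 65.2 | 50.5% | 0.288 |
| 20% | 58.0 | 46.7% | 0.305 |
| 30% | 50.8 | 42.7% | 0.327 |
| 40% | 43.5 | 38.5% | 0.353 |

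Most of the loss comes from the calendar split. Each 10% refusal removes about 0.10 × 72.5 ≈ 7 patients per arm.

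**4. Possible selection bias.** Let e be the share of an arm excluded, and g the amount by which excluded patients' mean ln UACR change exceeds that of retained patients, equal in both arms. An arm's retained mean is its full mean minus e × g, so the contrast shifts by (difference in e) × g. All inputs here are assumed.

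- 25% versus 15%, g = 0.3: 0.10 × 0.3 = 0.03, which is 0.03/0.29 ≈ 10% of the design effect.
- 25% versus 15%, g = 0.5: 0.10 × 0.5 = 0.05, which is 0.05/0.29 ≈ 17%.
- 30% versus 10%, g = 0.5: 0.20 × 0.5 = 0.10.
- Equal exclusion, same g: 0.

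The contrast's standard error at 72.5 per arm is √(2/72.5) = 0.166, so 0.03 to 0.05 is about 0.2 to 0.3 standard errors.

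**The case against.** A reader might infer that every decliner's Week 60 data are lost. The text does not establish this. The visit at which they leave is not fixed and could be Week 60, and Table 2 provides an end-of-treatment or early-discontinuation visit with UACR, then a follow-up visit. Values up to Week 47 would still enter a repeated-measures model.

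A reader might also infer that the double-dose groups are defined as switched patients and that the comparison is no longer randomised. The protocol gives labels, not definitions. Section 4.1.1 can be read as describing a cohort fixed by date, of which those receiving the new treatment are a part, and the SAP may settle it. The two-capsule rule favours the switched-only reading without proving it. The groups are subsets of randomised arms, so what may be lost is the protection of randomisation, to an unknown degree.

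Differential selection is possible, not shown. The conditions are met before any 24 mg exposure, after 3 mg plus allopurinol or placebo, and consent is given under blinding. Section 2.3 reports equal rates of creatinine elevation in both groups of the Phase 2a study.

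Two further objections stand. Appendix A 3 requires re-consent to the current form, which offers a reason for ending participation on refusal, so any fix must deal with it. Comparing by randomised arm regardless of switch answers a different question from the effect of 24 mg in those who take it, and so should not replace the named comparison. Nor is that comparison all the information on 24 mg: safety is summarised by treatment received (Section 9.4.3), and PK is sampled at Week 60 (Section 8.5).

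What the objection does not remove is the conflict in follow-up rules. Refusing a dosing regimen does not imply refusing follow-up.

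**Conclusion.** The concern holds in two limited parts.

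First, the rule for decliners conflicts with the principle in Sections 7.1 and 7.1.3. As written, patients willing to be followed may lose Week 60 and follow-up data. How many is unknown, because the documents give neither a refusal rate nor the timing of discontinuation.

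Second, on its plain reading the only named 12-month comparison is restricted by four post-randomisation conditions, so selection bias is possible. The shift of 0.03 to 0.05 ln units rests on assumed exclusion of 25% versus 15% and an assumed prognostic difference of 0.3 to 0.5; it illustrates scale and does not estimate the bias.

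The primary analysis precedes the switch and is untouched. The 12-month endpoints are secondary and outside the multiplicity control. The point is still worth correcting, because missing follow-up cannot be repaired later.

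**What to change.** 1. Reconcile Sections 1.2, 4.1.1, 4.1.2.9 and 6.1.1 with 7.1 and 7.1.3, so that declining the new regimen does not by itself end study follow-up. Invite decliners to continue scheduled visits, or modified follow-up, through Week 60 and the follow-up visit, unless they withdraw consent to follow-up. To meet Appendix A 3, let the re-consent form offer a follow-up-only option. Whether decliners remain on study treatment is for the clinical team to reconcile.

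2. In Section 9.4.2.2, keep the switched-patient comparison and state who belongs to each double-dose group and that it is subject to post-randomisation selection. Beside it, add a comparison by randomised arm (low dose versus placebo) among all patients whose Visit 9 was due on or after the local activation date, regardless of switch.

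**Cost.** Wording in a few sections and the consent form, one flag from the activation date, one more analysis, and some extra follow-up. The added comparison dilutes the 24 mg effect. For illustration, if 20% of the low-dose arm did not switch and had no effect at all (both assumed), 0.29 would become 0.29 × 0.80 ≈ 0.23. That is why it belongs alongside the named comparison and not in its place.
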